clomiphene citrate alone, metformin achieved a significantly higher ovulation rate than clomiphene citrate alone (20). These women were only followed for 35 days on metformin, but achieved a 35% ovulation rate in this period (20). Studies which systematically examined menstrual regularity in PCOS women on metformin over a longer period of time have noted substantial improvement. Regular cycles, suggestive of monthly ovulation, have ranged from 69-96%(17;21;22). Few studies have addressed the issue of pregnancy in PCOS women on metformin and these have been observational and limited by a small sample size. (17;23) A more complete discussion of these trials is found in discussion of the power analysis below under IV B. Sample Size.

The preliminary evidence suggests that metformin in PCOS women is well tolerated, results in spontaneous ovulation, and is without known adverse effects during early pregnancy. Recently a new sustained release form of metformin, metformin XR with brand name Glucophage XR, has become available, and while similarly efficacious in the treatment of type II diabetes as metformin, it has a more favorable side effect profile. There are no published reports of the efficacy and tolerability of metformin XR in women with PCOS.

III. Objectives

A. Primary Research Hypotheses

The primary hypothesis is that improving insulin sensitivity and inappropriate gonadotropin secretion in infertile women with polycystic ovary syndrome (PCOS) with metformin and clomiphene citrate is more likely to result in a live birth than treatment with Metformin alone or clomiphene alone.

NICHD Reproductive Medicine Network
PPCOS-Pregnancy in Polycystic Ovary Syndrome Protocol
Primary Outcome Measure

The primary outcome measure is the presence/absence of a live birth during the study period. The primary analysis of live birth rate within the three treatment conditions will employ an intent-to-treat approach. Hence, patients will be analyzed according to the treatment group to which they are assigned, even if they did not receive the intended treatment or received only a portion of it.

B. Safety Hypothesis

The hypothesis is that adverse event rates between regimens will be comparable.

Safety Measures

Safety measures will be the number and category of reported adverse events

C. Secondary Research Hypotheses

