Medication will be adjusted based on progesterone response and side effects. Medication may therefore be adjusted downwards or eliminated to control side effects. These adjustments can take place independently of the DCC by the P.I at each individual site. For instance, if a patient complains of gastrointestinal symptoms (anorexia, diarrhea, GERD, or abdominal discomfort) and evaluation suggests that medication may be responsible the metformin XR/placebo dose should be backed down by 1 tablet per day every week until symptoms subside. If this necessitates stopping medication completely, the patient will be excluded from further study and discontinued. If symptoms subside, after 1 week an attempt should be made to increase the dose by one tablet every 5 days up to 4 tablets a day. Adjustments will be noted on CRFs.

Responders:

Responders will be identified on the basis of an elevated progesterone level consistent with ovulation (Progesterone ≥ 5 ng/mL). One elevated weekly level ≥ 5 ng/mL is evidence of response (36). The rationale for this is that it may not be possible to determine a midluteal peak level, but that two-week levels may overlap the peak and be elevated but not reach peak levels. Therefore we have chosen a middle level between two other cited levels of ovulation, 3 ng/mL and 10 ng/mL. After two consecutive elevated progesterone levels or at the discretion of the investigator, a urine hCG level will be checked. If initial result is negative, continue weekly urine hCG levels until menses. Treatment with all medications will cease from the point hCG is detected. If

NICHD Reproductive Medicine Network
PPCOS-Pregnancy in Polycystic Ovary Syndrome Protocol

ovulatory based on serum progesterone levels, women will continue their medication through menses at the same dose and in the same regimen. After menses from an ovulatory cycle, the patient will again take clomiphene citrate/placebo days 3-7 of the cycle as well as the daily metformin XR/placebo. Responders will continue at the same dose until pregnancy, or until a total of six cycles or until 30 weeks is reached.

Nonresponders:

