An inquiry into concomitant medications will be made at the baseline visit as well as each subsequent visit. Use of an exclusionary agent which affects reproductive function or metabolism, such as an anti-diabetic agent, during the study will be prohibited. These medications include oral contraceptives, GnRH agonists and antagonists, antiandrogens, gonadotropins, anti-obesity drugs, somatostatin, diazoxide, insulin, and calcium channel blockers. However it is possible that the P.I. or other physician will prescribe progestins during the study due to abnormal bleeding/prolonged amenorrhea, which will not qualify as a reason for withdrawal. This list will be examined by the P.I. on a monthly basis to determine a suitable course of action. Potential interactions with study medications should also be checked. For instance multiple medications have been shown to increase peak serum levels of metformin (nifedipine, furosemide, and cationic drugs such as morphine, procainamide, triamterene), although half life of metformin is unaffected.

I. Reporting Adverse Events

All serious adverse events (SAE's) throughout study participation from the start of study drug through one week after the last dose of study medication must be reported. For patients who conceive, all SAEs from the start of study drug through delivery/termination must be reported. SAEs should be reported within 24 hours (or 1 business day) of learning of the event to DCRI Safety Surveillance at:

[contact] (telephone)

[contact] (fax)

DCRI Safety Surveillance will forward reportable events to the NICHD within 1 business day of receipt. The NICHD will report serious, drug-related events to the FDA and all RMN Protocol
08Jan2004

NICHD Reproductive Medicine Network
PPCOS-Pregnancy in Polycystic Ovary Syndrome Protocol
participating investigators according to regulatory guidelines. The NICHD will forward relevant safety information to the DSMB as needed. The P.I. will be responsible for notifying their IRB of SAEs in accordance with local guidelines.

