A serious adverse event is one that is fatal or immediately life-threatening, severely or permanently disabling, requires or prolongs inpatient hospitalization, overdose (intentional or accidental), congenital anomaly, pregnancy loss after 12 weeks gestation or any event so deemed as serious by the P.I. at each RMN site. If any serious event occurs and is thought to be related to the study medication, the study medication will be discontinued. Twenty-four hour unblinding will be available through the IVRS system to break the randomization code for the individual patient if this is required by the P.I. for proper treatment of the patient.

J. Study Medication Related Adverse Events (*Please refer to Appendix E for details*)

There are a number of adverse events that are potentially related to study medication.

Metformin

Gastrointestinal symptoms (diarrhea, nausea, vomiting, abdominal bloating, flatulence, metallic taste in the mouth and anorexia) are the most common reactions to metformin XR and approximately 30% more frequent in women with metformin XR compared to placebo treated patients. These symptoms will be managed with a step down decrease in the daily metformin XR dose (one tablet per day per week) until symptoms resolve.

These symptoms alone will not be a reason for withdrawal from the study unless a patient is unable to tolerate any dose of the medication.

There is a small risk of lactic acidosis among women taking this medication. This most commonly occurs in patients with poorly controlled diabetes and impaired renal function. Women with these pre-existing medical problems will be excluded from the RMN Protocol

NICHD Reproductive Medicine Network
PPCOS-Pregnancy in Polycystic Ovary Syndrome Protocol

protocol as per the exclusion criteria. There have been reports of lactic acidosis induced by exposure to iodine-containing radiocontrast agents, such as those used for an intravenous pyelogram or even for hysterosalpingogram, if there is intravasation. Metformin XR will be stopped prior to procedures involving exposure to radiocontrast agents to reduce the chance of developing lactic acidosis (one week prior to medication and resume one week after the test). The development of lactic acidosis for any reason will be a reason for discontinuing the study.

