Adverse Event Analysis: Adverse events will be categorized and percentage of patients experiencing adverse events and serious adverse events during the treatment period will be detailed. Chi-square tests will be performed to examine differences in the proportion of total and categories of adverse events within each treatment arm. For each DSMB report, a list and summary of the reported adverse events will be presented in a blinded fashion, unless otherwise formally requested.

C. Secondary Efficacy Measures

Although not powered to address the secondary outcome parameters, such analyses may provide important pilot data for powering future studies. Multiple logistic regression models will be used in analyses of secondary efficacy measures to evaluate the predictive value of treatment condition, clinical site (if needed), prior exposure to either clomiphene citrate or metformin XR, body mass index, and other explanatory variables on the secondary binary outcomes (e.g., abortion, ovulation). Generalized estimating equations approach will be used if there are multiple outcomes (eg., multiple ovulations) per patient to account correlation within patient. Examples of potential explanatory variables and covariates are: clinical site, prior exposure to either clomiphene citrate or metformin XR, body mass index, age, among others, total testosterone, insulin, proinsulin, and glucose values. Cox proportional hazards models and a Kaplan-Meier method will be applied to compare time to event (eg., cycles to first ovulation, cycles to first conception, cycles to pregnancy, weeks from viable pregnancy to live birth) between the treatment groups.

NICHD Reproductive Medicine Network
PPCOS-Pregnancy in Polycystic Ovary Syndrome Protocol

Due to the exploratory nature of these analyses, the level of significance for the secondary analyses will be set at 0.05 (two-tailed) to reduce the Type II error rate.

Definition of Secondary Measures

- Two different spontaneous abortion rates will be computed. The first is the number of spontaneous abortions over the number of patients who have conceived (defined by positive serum HCG) and the second is the number of spontaneous abortions over the number of patients who are pregnant (defined by detection of fetal heart beat).

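### The adverse-event percentages stop at the treatment period although SAEs are collected to delivery, and the second abortion rate counts losses that lie outside its denominator

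*Protocol*

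**What the plan says.** **Safety analysis.** Protocol V.B (Safety Measures) states that the percentage of patients with adverse events and "serious adverse events during the treatment period will be detailed". It then plans chi-square tests "to examine differences in the proportion of total and categories of adverse events within each treatment arm". That second sentence names no time window and does not mention SAEs. The objective behind it, III.B, reads "The hypothesis is that adverse event rates between regimens will be comparable"; the measure given there is the number and category of events reported, with no limit to a period.

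**Collection of SAEs.** IV.I requires that, for patients who conceive, "all SAEs from the start of study drug through delivery/termination must be reported". Appendix E repeats this window. The SAE definition in IV.I includes "congenital anomaly, pregnancy loss after 12 weeks gestation", and Appendix E lists both as well. Under Responders in IV.F, "Treatment with all medications will cease from the point hCG is detected". Figure 1 shows pregnancy as a separate phase without treatment.

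**Abortion rates.** V.C (Definition of Secondary Measures) defines two spontaneous abortion rates. The first divides the number of spontaneous abortions by the patients with a positive serum hCG. For the other, "the second is the number of spontaneous abortions over the number of patients who are pregnant (defined by detection of fetal heart beat" is the wording. The numerator is described in the same way for both. Under Pregnancy Visits, IV.F defines pregnancy as a conception with a heart beat, so the second denominator is a subset of the first.

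**The concern.** The protocol collects pregnancy-phase SAEs but describes a safety summary that, as worded, does not reach them. IV.B.4 makes the choice of combination therapy depend on there being no significant differences in adverse events. Congenital anomalies are a harm that a fertility trial should be able to show by arm, and the protocol names no analysis that does so.

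The second abortion rate would be read as the risk of loss once a heart beat has been seen. As written it mixes two sets of women. A difference between arms could then reflect only when losses occurred, which matters for the secondary hypothesis on first-trimester fetal demise (III.C, item 4).

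**Working it through.** The protocol states no figure on this point, so there is none to reproduce. Part A sets the timing rules side by side. Part B works through the ratio.

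**A. Which SAEs fall inside the treatment period?**

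Convention assumed here: gestation is counted from two weeks before conception, and term is 40 weeks.

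1. *Treatment period as time on drug.* Drug stops when hCG is detected. If that is at about 4 to 5 weeks' gestation (assumption), adding the one-week follow-up after the last dose reaches 5 to 6 weeks. A loss after 12 weeks, or an anomaly found at birth, comes later.
2. *Treatment period as the 30-week calendar phase.* The Synopsis uses the term this way under time to completion.
   - Conception in study week 2: 12 weeks' gestation at week 2 + 10 = 12, term at week 2 + 38 = 40. A late loss between weeks 12 and 30 counts; an anomaly found at term does not.
   - Conception in study week 20: 12 weeks' gestation at week 20 + 10 = 30. From here on, no late loss counts.
   - The share of late losses outside the window depends on when women conceive, which the protocol does not give.

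Scale, from the protocol's planning inputs (226 per arm; live birth 45%, 30% and 25%; 25% of conceptions lost):

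conceptions = 226 × live birth rate / (1 − 0.25)

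| Arm | Conceptions | Losses (25%) | Live births |
|---|---|---|---|
| Combination | 135.6 | 33.9 | 101.7 |
| Metformin | 90.4 | 22.6 | 67.8 |
| Clomiphene | 75.3 | 18.8 | 56.5 |
| Total | 301.3 | 75.3 | 226.0 |

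The documents give no anomaly rate. At an assumed 1, 3 or 5% of births, 226 × 0.01, 0.03 or 0.05 gives about 2, 7 or 11 anomalies over the whole trial.

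**B. The second abortion rate**

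Take 100 conceptions with 25 losses, the 25% assumed in IV.B.1. Let x be the losses before the heart beat. The documents do not give x, so a range is shown.

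- Rate as written: 25 / (100 − x)
- Loss after heart beat: (25 − x) / (100 − x)

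| Losses before heart beat | x | As written | Loss after heart beat |
|---|---|---|---|
| 0% | 0 | 25/100 = 25% | 25/100 = 25% |
| 20% | 5 | 25/95 = 26% | 20/95 = 21% |
| 60% | 15 | 25/85 = 29% | 10/85 = 12% |
| 80% | 20 | 25/80 = 31% | 5/80 = 6% |
| 100% | 25 | 25/75 = 33% | 0/75 = 0% |

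The two agree only when no loss precedes the heart beat; otherwise they move in opposite directions.

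Two arms with the same 25% total loss can be put in the wrong order:
- 30% of losses early (x = 7.5): written 25/92.5 = 27.0%; after heart beat 17.5/92.5 = 18.9%.
- 90% of losses early (x = 22.5): written 25/77.5 = 32.3%; after heart beat 2.5/77.5 = 3.2%.

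The ratio is also unbounded. If every loss came before the heart beat and a share q of conceptions were lost, it would equal q/(1 − q): 100% at q = 0.5 and 150% at q = 0.6.

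**The case against.** **On the window.** The limit to the treatment period sits in the descriptive sentence. The chi-square sentence carries no window, and III.B refers to reported events without restriction. DSMB reports list reported adverse events, and late SAEs still reach the sponsor. Pregnancy losses count against live birth, the primary endpoint analysed in all randomised women, and again in the first abortion rate. This all stands. A reader might infer that every anomaly and every late loss is shut out of the arm comparison; the documents do not support that. On the calendar reading some late losses fall inside, as might an anomaly diagnosed before birth, and the tests are not expressly limited. What remains is that the one stated window is narrower than both the objective and the collection rule, and that anomalies have no named arm comparison.

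**On the abortion rate.** The denominator could be read as naming the women among whom abortions are counted, which would make the rate sound. The analysis is declared exploratory, and the first rate is coherent. But the text uses the same unrestricted count for both rates, so a programmer following it would build the mixed ratio. A reader might also infer that logistic regression cannot be used. That does not follow: the planned model is for a patient-level yes/no outcome, which is valid among women with a heart beat.

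**On conditioning on conception.** It is tempting to replace both rates by loss per randomised woman. On the planning inputs this gives 33.9/226 = 15.0% for combination, 22.6/226 = 10.0% for metformin and 18.8/226 = 8.3% for clomiphene. Combination against clomiphene has z = 2.21 (p = 0.03), although loss per conception is 25% in both. The measure rises with the conception rate and would penalise the arm in which more women conceive.

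**Conclusion.** Both parts hold on the protocol's wording, and both are minor.

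The window in V.B conflicts with III.B and falls short of the collection rule in IV.I and Appendix E. On either reading of the treatment period, anomalies found at term lie outside it. Late losses lie outside it entirely on the on-drug reading, and in part on the calendar reading. The number of events concerned is small: about 2 to 11 anomalies on assumed rates of 1 to 5%.

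The second abortion rate, read literally, is not a proportion and overstates loss after the heart beat: 26, 29 or 31% as written, against 21, 12 or 6%. These figures rest on the protocol's 25% loss and on an assumed 20, 60 or 80% of losses before the heart beat. The direction of the error holds whenever any loss precedes the heart beat.

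The primary analysis and the first abortion rate are not affected.

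**What to change.** **V.B.** State that SAEs are summarised and compared by randomised arm over the full collection window, shown in two parts: on treatment (to one week after the last dose), and from conception to delivery or termination. Give the second part also per woman who conceived. Show congenital anomaly and loss after 12 weeks as separate categories, with exact tests where counts are sparse.

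**V.C.** Restrict the numerator of the second abortion rate to losses after a documented heart beat. Leave the first rate unchanged. If loss per randomised woman is shown, label it descriptive and note that it rises with the conception rate.

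**Cost.** A change of wording and a few extra tables from data already collected; no change to visits, forms or sample size.

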1. Age, body mass index, testosterone, insulin, glucose, and proinsulin levels will be significant predictors of ovulation and conception regardless of treatment.
2. Improvement in body mass index, testosterone, insulin, glucose, and proinsulin levels will be significant predictors of ovulation and conception regardless of treatment.
3. Treatment with metformin XR in combination with clomiphene citrate is more likely to result in singleton pregnancy compared to treatment with Metformin XR alone or clomiphene citrate alone. Singleton pregnancy is defined as presence of an intrauterine gestational SAC with a fetal pole and observable heart motion.
4. Treatment with metformin XR alone or in combination with clomiphene citrate will less likely lead to a first trimester intrauterine fetal demise than treatment with clomiphene citrate alone.

NICHD Reproductive Medicine Network
PPCOS-Pregnancy in Polycystic Ovary Syndrome Protocol

5. Treatment with metformin XR alone is more likely to result in ovulation (increased ovulation rate) compared to treatment with clomiphene citrate. Treatment with both is most likely to result in ovulation.
6. The shortest time to pregnancy will be with metformin XR/clomiphene citrate, followed by metformin XR, followed by clomiphene citrate.

D. Planned / Supplemental Analyses

A set of supplemental analyses/sensitivity analyses, will be conducted to evaluate the effect of treatments by excluding randomized patients who were later discovered to be not eligible, or by excluding patients who did not adhere to the assigned drug regimen.

[figure not shown]
IV. Study Design

A. Overview

The study will be a multicenter, double blind, randomized trial designed to determine the most effective method of achieving a live birth in infertile PCOS women. Patients will be randomized to one of three treatment strategies: 1) metformin XR alone, 2) clomiphene citrate alone, or 3) combined metformin XR and clomiphene citrate.

A1. Schematic of the study design: (see following page)

NICHD Reproductive Medicine Network
 PPCOS-Pregnancy in Polycystic Ovary Syndrome Protocol

NICHD Reproductive Medicine Network
PPCOS-Pregnancy in Polycystic Ovary Syndrome Protocol

A.2 Study Population

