There may be breaks in the protocol for both anticipated and unanticipated reasons. Subjects should be counseled that they should be seeking conception for the full potential 30-week period. If personal or professional commitments will result in more than a four-week break from the protocol, subjects should not be enrolled. A break or breaks, up to four weeks, from clomiphene citrate is allowable to facilitate timing of intercourse if there are other commitments. Metformin XR should be continued during this break. Urinary pregnancy tests can be dispensed to check weekly for pregnancy during these breaks. Longer break(s) should be an indication for dismissing the patient from the protocol as non-compliant.

Study Drug Termination Visit:

Patients who conceive, who complete the study without conception or who withdraw will undergo a study drug termination visit as close to their end of medication as possible. The goal of this visit is to determine that there has been no systemic adverse effects of the medication and to obtain follow up sera to identify predictive factors of success. This visit will consist of completion of a CRF, a brief physical which does not require a breast or pelvic exam, and repeat of the safety labs done at baseline. These safety labs include a CBC with platelets, a renal profile, and liver profile. Additionally,

NICHD Reproductive Medicine Network
PPCOS-Pregnancy in Polycystic Ovary Syndrome Protocol

1 ml of serum from one 7.5cc red top tube will be obtained for assay by the central lab.

Serum will be separated, aliquoted, and frozen at -20 to -80 degrees Centigrade until assay by the central lab. A repeat hirsutism assessment will be performed using the Ferriman Gallwey hirsutism scale. Additionally if the patient is pregnant, signed medical release forms should be obtained from the patient to obtain information about the pregnancy outcome-including forms for the prenatal caregiver and the intended hospital for delivery.

Pregnancy Visits:

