Conception will be confirmed, if suspected, by measurement of serum hCG. A urinary hCG may be sent as an initial screen. Conceptions will be followed by the serial rise of serum hCG and when a threshold level is obtained (2,000-4,000 mIU/mL), ultrasound will be utilized to determine location of the conception and number of implantation sites. Patients who conceive will be followed at the site until the pregnancy has advanced to the point of determining the number of gestational sacs, their location, and fetal viability as determined by visualization of fetal heart motion by ultrasonography. A conception with fetal heart beat is defined as pregnancy. At this point, approximately 6-8 weeks after conception, women will be referred to their prior or referring practitioner, or to an appropriate health care provider. Patients will be reminded to continue their prenatal vitamin or Folic Acid during pregnancy and provided with counseling about prenatal care. Women will be followed throughout pregnancy to determine the abortion rate and through delivery to determine pregnancy outcome. Patients will be informed to notify study personnel of the outcome of the pregnancy. Phone contacts will be initiated if the patient has not contacted study personnel by six weeks beyond the original estimated

NICHD Reproductive Medicine Network
 PPCOS-Pregnancy in Polycystic Ovary Syndrome Protocol

date of confinement. Delivery records will be requested to determine the birth weight, length of gestation, and any perinatal complications of mother or infant. If delivery records are not available, patient self-report will be acceptable, however, every effort will be made to obtain records.

Unblinding of Medication Assignments:

Study medication assignments will not be routinely unblinded until the results of the study have been released. Emergency unblinding will be at the discretion of the site P.I.

Timeline for Proposed Protocol

The timeline below is a conservative estimate of the time needed to complete the trial, analyze the data, and achieve publication of the primary publication summarizing the results of the trial. The study should be completed, including pregnancy outcome in all randomized women by year four and data analysis complete by the end of that year.

Preparation and submission of the first article should be achieved by the fifth year of the grant.

	Year 1	Year 2	Year 3	Year 4	Year 5
Protocol Completion					
Subject Recruitment					

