- An ovulation will be defined as an elevated weekly progesterone level separated by at least one week with a nonovulatory progesterone level. A binary variable indication whether the patient ovulated or not will be created for each cycle. Furthermore, cycles to first ovulation will be used as time to event variable.
- Time to pregnancy is defined as the number of cycles required to achieve a viable implantation (detection of fetal heart beat). Weeks from pregnancy to live birth will also be used as a time to event variable for patients who did not have miscarriages.
- Conception. Conception is confirmed by a positive serum hCG value. Cycles to first conception will be used as a time to event variable.

E. Drop outs/Treatment Failures

Dropouts, either by patient choice or physician recommendation due to adverse effects or poor compliance will be analyzed by intention to treat as treatment failures. Subjects who have completed 30 weeks or 6 treatment cycles without a pregnancy will also be considered as treatment failures. Subjects who conceive and are lost to follow up will be considered as a treatment success. It is considered unlikely that the patients will be lost to follow-up after a conception on a treatment regimen.

NICHD Reproductive Medicine Network
PPCOS-Pregnancy in Polycystic Ovary Syndrome Protocol

F. Interim Analysis

Analysis Plan: An interim analysis will be conducted on the primary endpoint when 50% of the study participants have completed treatment. The primary analysis described above will be performed and the O'Brien-Fleming (1979) method will be applied to adjust for at the number of looks at the primary endpoint. The interim analysis should also provide a detailed summary of adverse events reported. The critical value for the primary analysis will be specified in the detailed analysis plan. The results of the interim analysis will be submitted to the Data Safety and Monitoring Committee (DSMC). The interim analysis results will be presented in a blinded fashion to the DSMC, who will then evaluate the findings to determine whether the trial should be continued, modified, or discontinued.

Stopping Rules: The stopping rule for the O'Brien-Fleming method compares the statistic Z_i with $Z^*(N/i)^{.5}$, where Z^* is the critical value for the significance level (.05), N is the total number of analyses ($N = 2$) and i is the analysis number (for the one planned analysis, $i = 1$).

VI. DISCLOSURE OF DATA

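### Kaplan-Meier for cycles to pregnancy would slightly overstate the six-cycle pregnancy probability if losses before fetal heart beat are censored

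*Protocol*

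**What the plan says.** Section V.C (Secondary Efficacy Measures) states: "Cox proportional hazards models and a Kaplan-Meier method will be applied to compare time to event (eg., cycles to first ovulation, cycles to first conception". The list goes on to cycles to pregnancy and to weeks from viable pregnancy to live birth. The definitions later in V.C read: "Time to pregnancy is defined as the number of cycles required to achieve a viable implantation (detection of fetal heart beat". Section IV.F, under Pregnancy Visits, agrees: "A conception with fetal heart beat is defined as pregnancy". A positive hCG alone is a conception and not yet the event.

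Two other parts of Section IV.F settle what happens at conception. Under Responders: "Treatment with all medications will cease from the point hCG is detected". Under Study Drug Termination Visit: "Patients who conceive, who complete the study without conception or who withdraw will undergo a study drug termination visit". The protocol describes no return to treatment after an early loss.

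The endpoint serves secondary hypothesis 6 in Section III.C: "The shortest time to pregnancy will be with metformin XR/clomiphene citrate, followed by metformin XR, followed by clomiphene citrate". Section V.C labels the secondary analyses exploratory, says the study is not powered for them, and expects them to help plan later studies.

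Section V.E adds: "Dropouts, either by patient choice or physician recommendation due to adverse effects or poor compliance will be analyzed by intention to treat as treatment failures". It does not say to which endpoints this applies.

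**The concern.** A woman who loses a conception before a heart beat is off drug, has had her termination visit and accrues no further treatment cycles. On the text as it stands, she cannot then have the event on study treatment. Conventional Kaplan-Meier would censor her at her last cycle. That treats her as someone who would go on to a heart beat at the same rate as women still being treated. The resulting 1-KM is not the proportion of randomised women who reach a heart beat within six cycles. It is the larger proportion expected if early loss could not happen.

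The excess grows with the conception rate. With similar loss and dropout in all arms it is therefore largest where most women conceive, which the protocol expects to be the combination arm. At stake is a reported percentage, and the visual gap between curves, for an endpoint that may inform the planning of later trials.

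**Working it through.** The protocol gives no figure for cycles to pregnancy, so there is none to reproduce. The planning live-birth rates used here are those behind its sample size. The 45% versus 30% row (two-sided alpha 0.025, 80% power, no continuity correction) recomputes to the stated 197 per arm before dropout.

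**Inputs**
- Live birth 45% combination, 30% metformin, 25% clomiphene (IV.B.5).
- Pregnancy loss 25% of conceptions, equal in all arms (IV.B.1).
- Six treatment cycles (IV.D); 226 women per arm (IV.B.6).
- Share q of conceptions lost before heart beat: not given. Assumed range 5% to 25%. The upper end means that every planned loss occurs before a heart beat.
- Assumed: constant conception probability per cycle and, in this step, no dropout.

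**Step 1. Conception.** Six-cycle conception is live birth / 0.75: 60%, 40% and 33.3%. The per-cycle probability is c = 1 − (1 − conception)^(1/6):
- combination 1 − 0.40^(1/6) = 0.1416
- metformin 1 − 0.60^(1/6) = 0.0816
- clomiphene 1 − 0.667^(1/6) = 0.0653

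**Step 2. Two estimates of pregnancy by cycle six.**
- Cumulative incidence, with an early loss counted as never pregnant: (1 − q) × [1 − (1 − c)^6].
- 1-KM with early losses censored: 1 − [1 − c(1 − q)]^6.

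For the combination arm at q = 10%, cumulative incidence is 0.90 × 0.60 = 54.0%. 1-KM is 1 − (1 − 0.1275)^6 = 55.9%. The excess is 1.9 points.

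| q | Combination: cumulative incidence / 1-KM | Excess, combination | Excess, metformin | Excess, clomiphene |
|---|---|---|---|---|
| 5% | 57.0% / 58.0% | 1.0 | 0.4 | 0.3 |
| 10% | 54.0% / 55.9% | 1.9 | 0.7 | 0.5 |
| 15% | 51.0% / 53.7% | 2.7 | 1.0 | 0.7 |
| 25% | 45.0% / 49.0% | 4.0 | 1.5 | 1.0 |

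As a check, at q = 25% the cumulative incidence in the combination arm returns the planned 45% live-birth rate, as it must.

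**Step 3. Effect on the arm difference.** The standard error of a difference is √{[p1(1 − p1) + p2(1 − p2)]/226}. For combination minus clomiphene:
- q = 10%: the difference moves from 24.0 to 25.4 points, about 0.31 of its standard error (4.5 points).
- q = 15%: from 22.7 to 24.7 points, about 0.44 standard errors.
- q = 25%: from 20.0 to 23.0 points.

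**Step 4. Hazard ratio.** With an equal loss share, (1 − q) cancels from the ratio of per-cycle pregnancy probabilities. Combination to clomiphene is 0.1416 / 0.0653 = 2.17 at every q.

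**Step 5. An alternative within Kaplan-Meier.** If women with an early loss stay in the risk set as non-events to cycle six, Kaplan-Meier returns exactly the cumulative incidence, and the excess disappears.

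**The case against.** The strongest reply is that the protocol names methods and states no censoring rule. Risk-set rules commonly belong in the analysis plan, which is not at hand and may already deal with early losses. That stands as far as it goes: the overstatement is conditional on conventional censoring. What the protocol does fix is the event, the Kaplan-Meier method, a time scale in treatment cycles and the end of treatment at hCG. Together these make censoring the default reading.

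A reader might also infer four stronger points. The document supports none of them.

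- *Kaplan-Meier can only censor these women.* Step 5 shows otherwise.
- *The Cox comparison is biased.* With early losses censored, Cox estimates a cause-specific hazard ratio, which is a legitimate comparison of arms.
- *V.C and V.E contradict each other on dropouts.* V.E names no endpoint, and V.C states no dropout-censoring rule. Counting the planned 15% dropout as failures (per-cycle dropout 1 − 0.85^(1/6) = 0.027) lowers the combination figure at q = 10% to 51.1%, against a 1-KM of 55.9%. That gap of 4.8 points is an overstatement only if the failure rule is meant to apply here, or if dropout is informative. Dropout does not prevent pregnancy, so coding it as a competing event is a choice of estimand and not a correction.
- *The excess is always largest in the combination arm.* This held for equal dropout, and for every arm-specific loss share tried, up to 50% with clomiphene against 10% in the other arms. Secondary hypothesis 4, that metformin regimens "will less likely lead to a first trimester intrauterine fetal demise than treatment with clomiphene citrate alone", therefore does not by itself overturn the ordering. Unequal dropout can: if dropouts count as failures, q = 10%, and dropout is 25% with metformin and 10% elsewhere (assumed), the excess is 4.3 points for metformin and 3.8 for the combination.

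It is also an inference that a woman cannot return to treatment after an early loss. The protocol does not say so outright; it only describes no such return.

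**Conclusion.** The point holds as a minor one. A loss before heart beat competes with the event of cycles to pregnancy. A conventionally censored 1-KM curve would overstate six-cycle pregnancy by about 1 to 4 points in the combination arm and 0.3 to 1.5 points in the single-agent arms. This rests on the planning rates, a constant per-cycle conception probability, an equal early-loss share assumed between 5% and 25%, and no return to treatment after an early loss. At 10% to 15% early loss the combination-clomiphene difference shifts by 0.3 to 0.4 of its standard error, which would seldom change a conclusion. The cause-specific Cox comparison stands, and the primary chi-square test of live birth is unaffected. The wording of V.E is an ambiguity to clear up, not a demonstrated contradiction.

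**What to change.** In Section V.C, for cycles to pregnancy:

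1. Report the cumulative incidence of pregnancy with loss before fetal heart beat as a competing event, in place of 1-KM. Keeping such women in the risk set as non-events to cycle six is equivalent.
2. Keep the Cox model and label it the cause-specific analysis.
3. State whether the dropout-as-failure rule in V.E applies to the time-to-event endpoints or only to the binary outcome.

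The cost is a few sentences and a few lines of code. The hCG, ultrasound and withdrawal data needed are already planned. The one visible effect is that reported pregnancy percentages become slightly lower.
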